### **11.2.2.2 Reporting within 24 hours of knowledge of the event.**

#### **11.2.2.2(A) Report to the NCI DCP Medical Monitor within 24 hours:**

Contact the DCP Medical Monitor by phone within 24 hours of knowledge of the event.

[name]  
NCI/Division of Cancer Prevention  
[name]  
[name] (For FEdEX, [name])  
[contact]  
[contact]  
Email: [contact]

Include the following information when calling the Medical Monitor:

- Date and time of the SAE
- Date and time of the SAE report
- Name of reporter
- Call back phone number
- Affiliation/Institution conducting the study
- DCP protocol number
- Title of protocol
- Description of the SAE, including attribution to drug and expectedness

#### **11.2.2.2(B) Report to the Consortium Lead Organization (CLO) PI ([name]) within 24 hours of knowledge of the event:**

Report all SAEs to the Consortium Lead Organization PI ([name]) within 24 hours of knowledge of the event. The same information reported to the DCP Medical Monitor should be provided to the CLO via email, phone or fax within 24 hours of knowledge of the event.

#### **11.2.2.2(C) Report to the drug supplier (Bayer) within 24 hours of knowledge of the event:**

Report all SAEs to Bayer ([contact], email: [contact]) within 24 hours of knowledge of the event. The same information reported to the DCP Medical Monitor should be provided to Bayer via fax or email, within 24 hours of knowledge of the event ([contact], email: [contact]).

### **11.2.2.3 Reporting within 48 hours of knowledge of the event:**

11.2.2.3 (A) FAX or email the written SAE reports to the DCP Medical Monitor within 48 hours of learning of the event using the paper SAE form. The SAE forms should be obtained at [http://prevention.cancer.gov/sites/default/files/uploads/clinical\\_trial/SAE-form.pdf](http://prevention.cancer.gov/sites/default/files/uploads/clinical_trial/SAE-form.pdf).

11.2.2.3 (B) The written SAE reports will also be FAX'ed to DCP's Regulatory Contractor, CCS Associates, at [name] ([contact]), email: [contact]

11.2.2.3 (C) The written SAE report will also be faxed or emailed to the Consortium Lead Organization PI ([name]), at [contact] or emailed to [[contact]](mailto:[contact]).

It is the responsibility of the CLO to inform the Lead Protocol PI upon receipt of the report from the organization experiencing the event.

11.2.2.3 (D) The written SAE report will also be faxed or emailed to Bayer [contact], email: [contact]

11.2.2.4 The DCP Medical Monitor and regulatory staff will determine which SAEs require FDA submission.

11.2.2.5 The Lead Organization and all Participating Organizations will comply with applicable regulatory requirements related to reporting SAEs to the local IRB/IEC, and to the DSMB.

#### 11.2.2.6 Follow-up of SAE

Site staff should send follow-up reports as requested when additional information is available. Additional information should be entered on the DCP SAE form in the appropriate format. Follow-up information should be sent to DCP as soon as available. SAEs related to the study agent will be followed until resolved. The Lead Organization and all Participating Organizations will comply with applicable regulatory requirements related to reporting SAEs to the local IRB/IEC, and to the DSMB.

## 12. STUDY MONITORING

### 12.1 Data Management

The study PI will identify a dedicated data manager who will be responsible for the correct management of the trial conduct. In particular, he/she will periodically verify subject eligibility, informed consent signatures, accuracy and completeness of CRFs and congruency with all source documents (including laboratory print outs, drug inventory and destruction logs). All source documents will be collected in individual binders, stored in locked cupboards and accessible for any audit or inspection by authorized personnel. Should the PI change, custody of the records may be transferred to another competent person who will accept responsibility for those records.

Written notice of such event has to be given to the local Ethics Committee at least one month in advance. This study will report clinical data using the Data Management Initiative (DMI) web-based application managed by the Consortium Biostatistics and Data Management Core. Data Management Initiative (DMI) infrastructure has been developed in the Division of Quantitative Sciences (DQS), MD Anderson Cancer Center. This infrastructure supplies integrated database and software services for web-based data collection, randomized treatment assignment, reporting, query, data download, and data quality management. The DMI will be the database of record for the protocol and subject to NCI and FDA audit. All DMI users will be trained to use the DMI system and will comply with the instructions in the protocol-specific "DMI User Manual" as well as applicable regulatory requirements such as 21 CFR; Part 11. Data management procedures for this protocol adheres to the Data Management Plan (DMP) contract HH2620100034I for Consortia 2012.

### 12.2 Case Report Forms

Participant data will be collected using protocol-specific case report forms (CRF) developed from the standard set of DCP Chemoprevention CRF Templates and utilizing NCI-approved Common Data Elements (CDEs). The approved CRFs will be used to create the electronic CRF (e-CRF) screens in the DMI application. Site staff will enter data into the e-CRF. Amended CRFs will be submitted to the DCP Protocol Information Office for review and approval. Approved changes will be programmed into the DMI database by the Consortium Biostatistics and Data Management Core.

### **12.3 Source Documents**

Source documentation will include only those documents containing original forms of data, including clinic charts, shadow files, hospital charts, and physician notes. Data recorded directly on the CRFs designated as source documents (i.e., no prior written or electronic record of data) will be considered source data. All other data recorded on the CRFs will not be considered source documentation.

### **12.4 Data and Safety Monitoring Plan**

The Data and Safety Monitoring Plan for the MD Anderson Consortium is on file at the DCP. This study will be monitored by the MDACC Data and Safety Monitoring Board, the data and safety monitoring board of record for this study. The Data Safety and Monitoring Board (DSMB) reports to the President, or his designee, as the on-campus representative of The University of Texas Board of Regents. It oversees the data and patient safety issues for randomized clinical trials that originate at MD Anderson; that are coordinated or analyzed by MD Anderson and are not being monitored by any other DSMB; or have been designated as requiring DSMB monitoring at the request of the IRB, the CRC, or institution. The primary objectives of the DSMB are to ensure that patients' rights pertaining to participation in a research study are protected, and that patients' interests are prioritized over the interests of the scientific investigation. Responsibilities include:

- (a) Review interim analyses of outcome data (prepared by the study statistician or other responsible person at the time points defined in the study) approved by the IRB and additional time points as determined by the DSMB, and to recommend, if necessary, whether the study needs to be changed or terminated based on these analyses;
- (b) Determine whether, and to whom, outcome results should be released prior to the reporting of study results;
- (c) Review interim toxicity data and efficacy of treatment;
- (d) Review major research modifications proposed by the investigator or appropriate study committee prior to implementation (e.g., termination, dropping an arm based on toxicity results from the study or results of other studies, increasing target sample size).

Refer to the Data and Safety Monitoring Plan for the MD Anderson Consortium on file at the DCP for further details.

### **12.5 Sponsor or FDA Monitoring**

The Sponsor, members of the Ethics Committee, representatives of the Italian Ministry of Health or representatives of the national Competent Authority, the NCI, DCP (or their designee), pharmaceutical collaborator (or their designee), or FDA may monitor/audit various aspects of the study. These monitors will be given access to facilities, databases, supplies and records to review and verify data pertinent to the study.

## 12.6 Record Retention

Clinical records for all participants, including CRFs, all source documentation (containing evidence to study eligibility, history and physical findings, laboratory data, results of consultations, *etc.*), as well as IRB records and other regulatory documentation will be retained by the Investigator in a secure storage facility in compliance with Health Insurance Portability and Accountability Act (HIPAA), Office of Human Research Protections (OHRP), Food and Drug Administration (FDA) regulations and guidances, and NCI/DCP requirements, unless the standard at the site is more stringent. The records for all studies performed under an IND will be maintained, at a minimum, for two years after the approval of a New Drug Application (NDA). For NCI/DCP, records will be retained for at least three years after the completion of the research. NCI will be notified prior to the planned destruction of any materials. The records should be accessible for inspection and copying by authorized persons of the Food and Drug Administration. If the study is done outside of the United States, applicable regulatory requirements for the specific country participating in the study also apply.

## 12.7 Cooperative Research and Development Agreement (CRADA)/Clinical Trials Agreement (CTA)

The agent(s) supplied by DCP, NCI, used in this protocol, is/are provided to the NCI under a Collaborative Agreement (CRADA, CTA) between the Pharmaceutical Company(ies) (hereinafter referred to as Collaborator(s)) and the NCI Division of Cancer Prevention. Therefore, the following obligations/guidelines, in addition to the provisions in the "Intellectual Property Option to Collaborator@ contained within the terms of award, apply to the use of Agent(s) in this study:

12.7.1 Agent(s) may not be used for any purpose outside the scope of this protocol, nor can Agent(s) be transferred or licensed to any party not participating in the clinical study. Collaborator(s) data for Agent(s) are confidential and proprietary to Collaborator(s) and shall be maintained as such by the investigators. The protocol documents for studies utilizing investigational agents contain confidential information and should not be shared or distributed without the permission of the NCI. If a patient participating on the study or participant's family member requests a copy of this protocol, the individual should sign a confidentiality agreement. A suitable model agreement can be downloaded from the DCP website.

12.7.2 For a clinical protocol where there is an Investigational Agent used in combination with (an) other investigational Agent(s), each the subject of different collaborative agreements, the access to and use of data by each Collaborator shall be as follows (data pertaining to such combination use shall hereinafter be referred to as "Multi-party Data").

12.7.3 NCI must provide all Collaborators with prior written notice regarding the existence and nature of any agreements governing their collaboration with NIH, the design of the proposed combination protocol, and the existence of any obligations that would tend to restrict NCI's participation in the proposed combination protocol.

12.7.4 Each Collaborator shall agree to permit use of the Multi-Party Data from the clinical trial by any other Collaborator solely to the extent necessary to allow said other Collaborator to develop, obtain regulatory approval, or commercialize its own investigational agent.

12.7.5 Any Collaborator having the right to use the Multi-Party Data from these trials must agree in writing prior to the commencement of the trials that it will use the Multi-Party Data solely for development, regulatory approval, and commercialization of its own investigational agent.

12.7.6 Clinical Trial Data and Results and Raw Data developed under a collaborative agreement will be made available exclusively to Collaborator(s), the NCI, and the FDA, as appropriate. All data made available will comply with HIPAA regulations.

12.7.7 When a Collaborator wishes to initiate a data request, the request should first be sent to the NCI, who will then notify the appropriate investigators of Collaborator's wish to contact them.

12.7.8 Any manuscripts reporting the results of this clinical trial must be provided to DCP for immediate delivery to Collaborator(s) for advisory review and comment prior to submission for publication. Collaborator(s) will have 30 days (or as specified in the CTA) from the date of receipt for review. Collaborator shall have the right to request that publication be delayed for up to an additional 30 days in order to ensure that Collaborator's confidential and proprietary data, in addition to Collaborator(s)'s intellectual property rights, are protected. Copies of abstracts must be provided to DCP for forwarding to Collaborator(s) for courtesy review as soon as possible and preferably at least three days prior to submission, but in any case, prior to presentation at the meeting or publication in the proceedings. Press releases and other media presentations must also be forwarded to DCP prior to release. Copies of any manuscript, abstract, and/or press release/ media presentation should be sent to:

Head, DCP Protocol Information Office  
[name]  
[name]  
E-mail: [NCI\\_DCP [contact]](mailto:NCI_DCP [contact])

The Protocol Information Office will forward manuscripts to the DCP Task Order Monitor for distribution to the Collaborator(s). No publication, manuscript or other form of public disclosure shall contain any of Collaborator's confidential/proprietary information.

Participant data will be collected using protocol-specific case report forms (CRFs) developed from the standard set of DCP Chemoprevention CRF Templates and utilizing NCI-approved Common Data Elements (CDEs).

## 13. STATISTICAL CONSIDERATIONS

### 13.1 Study Design/Description

The trial will be a randomized double-blind placebo controlled phase IIb study. Patients will be randomized to receive either aspirin 100 mg/day or matched placebo for 1 year. Analysis will be performed according to intention to treat principle and then according to efficacy.

The primary endpoint will be the difference of the sum of longest diameters of subsolid (non-solid or partially solid) lung nodules in a person-specific analysis.

The sample size has been calculated assuming a -0.2 mm average reduction of the sum of the longest diameter of all non-solid and partially-solid lesions at 12 months with respect to baseline in the placebo arm vs. an expected average reduction of -1.0 mm in the aspirin group.

## 13.2 Randomization/Stratification

In order to keep at minimum the imbalance in treatments a stratified blocked randomization strategy will be used considering only the relevant prognostic factors. Subjects will be stratified according to screening vs non screening CT scan, gender, smoking habits (current versus former smokers) and nodule type (non solid versus partially solid nodules). A blocked randomization will be done within each stratum. Other possible prognostic factors are age, the number of lesions, their volume doubling time and their size but since there is no evidence that they affect the response probability they will be included just in a stratified analysis, not during the randomization process.

Justification of stratification:

Stratification by nodule type and smoking status is planned because both non solid type and active smoking are associated with the risk of developing lung malignancies and their natural history, while stratification by screening vs non screening CT scan, and gender are conservative. The effect of aspirin has been variable in men and women for the prevention of certain conditions.

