The University of Texas MD Anderson Cancer Center launched its Lung Cancer Screening Program in 2011. To date, nearly 800 patients have been screened averaging approximately 20-30 screened patients per month. An additional resource for screening CTs is the active protocol entitled "*Biospecimen Banking and Biomarker Validation for Lung Cancer Early Detection in Cohort Receiving Low Dose Helical Computed Tomography Screening*" which has 194 patients currently enrolled. Although literature indicates the frequency of eligible lesions is approximately 30%, MDACC's experience is slightly less at 10% (2-3 patients per month) identified by low dose screening CT scan. From this population, it is anticipated the Lung Cancer Screening program may enroll less than 1 eligible patient per month after evaluation of other eligibility criteria. However, with the inclusion of lesions identified by diagnostic CT scan, MDACC's large cancer survivor population offers a larger pool of potentially eligible patients undergoing CTs for surveillance.

Based on the recent knowledge on the chemopreventive effect of Aspirin on lung cancer, we intend to evaluate the effect of low dose Aspirin (100 mg/day) on non solid and partially solid nodules identified in high risk volunteers submitted to annual low dose CTs among the ongoing screening programs at EIO and MDACC.

In addition, we will include subjects undergoing CT outside the context of a screening program with a subsolid nodule confirmed by pulmonary CT scan.

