### MD Anderson

For US clinical supplies, the packaged drug will be labeled in US English by the NCI DCP repository, MRIGlobal. The NCI DCP repository will distribute the clinical material to MDACC.

NCI, DCP-supplied agents may be requested by the Investigator (or their authorized designees) at each Organization. DCP guidelines require that the agent be shipped directly to the institution or site where the agent will be prepared and administered. DCP does not permit the transfer of agents between institutions (unless prior approval from DCP is obtained). DCP does not automatically ship agents; the site must make a request. Agents are requested by completing the DCP Clinical Drug Request form (NIH-986) (to include complete shipping contact information) and faxing or mailing the form to the DCP agent repository contractor:

[name]  
MRIGlobal  
DCP Repository  
[name]  
[name]  
[contact]  
[contact]  
Emergency [contact]

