## 6.6 Packaging and Labeling

Aspirin and matching placebo will be provided to EIO by Bayer Europe as a bulk shipment, but labeled and packaged by an external Pharmacy where they will be stored until delivery. An undisclosed randomization list will be provided by the statistician to the dedicated Pharmacist. Each package consists of a 7-month supply of the drug or placebo. Each box contains seven bottles with 30 tablets each. Each box will be labeled with the following information: EIO study number (S-XXX), randomization number (3 digits), PI's name and phone number, number of total doses, daily dose and schedule, lot numbers and expiring dates, specific instruction such as storage temperature, indication to keep the bottle out of reach of children. Subject's identification number will not be reported on drug packages. The same instructions will be stuck in the external part of the box package. Half of the label will be removed from the box and stuck into the drug delivery CRF to confirm appropriate drug has been administered to the subject.

For clinical supplies in the US, the NCI, DCP repository (MRIGlobal) will perform the product labeling, using US English labels, and will store the product for distribution to MDACC.

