### *Randomization:*

Participants will be assigned a randomization number once the following has been accomplished: eligibility has been verified at the site level, eligibility has been confirmed by the site PI, and eligibility CRF has been entered into the DMI web application. The randomization number will be generated by the database and assigned to the participant. Refer to Section 13.2 for details of randomization.

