#### **Assessment of lung nodules with low dose CT scan at MDACC**

Investigations will be performed with low-dose CT scans (average effective dose <1.5 mSv, without contrast medium), with a multidetector (64 slices) CT scanner (CT750 HD, General Electric Healthcare, USA) with the following parameters:

- 120 Kvp, noise modulation, Radiation dose < 3mGy for standard size patient.

Matrix 512x 512

- 2.5 mm, 1.25 mm and 0.625 mm thickness

Soft tissue and lung algorithm

- single breath, in respiratory apnea
- retro-reconstruction at 50% interval
- multiplannar reconstruction at scanner.3-dimensional volume reconstruction performed with dedicated software .

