## 13.3 Accrual and Feasibility

A sample size of 128 patients (64 per arm) achieve 80% power to detect a difference of -0.8 mm between the null hypothesis that both groups average reduction is -0.2 mm and the alternative hypothesis that the average reduction of target nodules in the aspirin group is -1.0 mm, with estimated effect size of 0.5 (common standard deviations of 1.6 mm) and with a significance level (alpha) of 0.05 using a two-sided two-sample t-test. The average shrinkage in the placebo arm is derived from the Budesonide trial.

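### Site (EIO or MDACC) is neither a stratification factor nor an analysis term, although CT settings and recruitment pools differ by site; pre-specify it as a fixed effect

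*Combined protocol and SAP*

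**What the plan says.** Section 13.2 sets up blocked randomization within strata: "Subjects will be stratified according to screening vs non screening CT scan, gender, smoking habits (current versus former smokers) and nodule type". Four two-level factors give 16 strata. The block size is not stated. Age, number of lesions, volume doubling time and lesion size are left to a stratified analysis. Site appears in neither list.

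Section 13.4 compares mean one-year change between arms with a t-test and no covariates. The 13.5 model contains arm, visit, smoking history and age, and no site term.

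Section 7.6 gives separate low-dose CT settings by site. EIO uses a fixed 30 mA, 2.5 mm slices and a soft tissue algorithm. MDACC uses noise modulation, "2.5 mm, 1.25 mm and 0.625 mm thickness", and both soft tissue and lung algorithms. Sections 2.3 and 4.4 describe the pools. EIO draws mainly on Cosmos 2 screening volunteers. MDACC expects few participants from screening and points to its cancer survivors, a "larger pool of potentially eligible patients undergoing CTs for surveillance".

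On supply, section 6.6 says: "Each box will be labeled with the following information: EIO study number (S-XXX), randomization number (3 digits"). Section 6.8 says: "The randomization number will be generated by the database and assigned to the participant". US stock is labelled and stored separately for MDACC.

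**The concern.** Section 13.2 keeps CT source and gender as factors on conservative grounds. Site has at least as good a claim. It is linked to how the images behind the millimetre endpoint are acquired, and to who carries the nodules and so perhaps to how those nodules evolve.

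With site in neither the randomization nor the model, two things follow. Any between-site difference in mean change stays in the error term. And a chance excess of MDACC participants in one arm goes uncorrected into the aspirin-placebo difference.

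**Working it through.** **The plan's own figure.** Section 13.3 states: "A sample size of 128 patients (64 per arm) achieve 80% power to detect a difference of -0.8 mm", with SD 1.6 mm, "with a significance level (alpha) of 0.05 using a two-sided two-sample t-test". With 64 per arm the noncentrality is 0.5 × √(64/2) = 2.83 on 126 degrees of freedom, and power is 80.1% (79.5% at 63 per arm). The sample size reproduces and does not depend on site. The standard error of the difference is 1.6 × √(2/64) = 0.28 mm.

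**Assumptions not in the documents.**
- MDACC share p = 10-33%. The upper end is the rate in 4.4 of about 1 per month over 42 months: 42/128 = 33%. Section 2.3 says less than 1 per month, and 4.4 projects about 128 randomized from the EIO pool alone, so the share could be low.
- Difference between sites in mean change d = 0.3-1.0 mm.
- For the simulations: blocks of 4, a screening share of 85% at EIO and 25% at MDACC, 50% current smokers and 30% partially solid nodules. The 35% women is from 4.3.

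**Chance imbalance under 13.2 as written (simulated, 20% share).** The arms differ by 6 or more MDACC participants in about 18% of trials if the MDACC count varies at random around 26. The figure is about 22% if the count is fixed at 26. The SD of the between-arm difference in MDACC share is about 6.3 percentage points, and 5% of trials exceed about 12.5 points.

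**Shift in the estimate.**
- Ignoring stratification, the SD of the difference in share is √(2p(1−p)/64): 5.3 points at p = 0.10 and 8.3 points at p = 0.33.
- A 2-SD imbalance then shifts the estimate by 2 × 0.053 × 0.3 = 0.03 mm up to 2 × 0.083 × 1.0 = 0.17 mm.
- With the simulated 6.3 points, which respects the stratification, the range is 2 × 0.063 × 0.3 = 0.04 mm to 2 × 0.063 × 1.0 = 0.13 mm.

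**Power with site in the model.**
- Share of variance explained = p(1−p)d²/1.6²: 0.10 × 0.90 × 0.09/2.56 = 0.3%, up to 0.33 × 0.67 × 1.0/2.56 = 8.6%.
- The residual SD is 1.6 × √(1 − share), or 1.597 to 1.529 mm. Power is 80.3% to 83.6%.
- With no site effect and one degree of freedom fewer (125), power is still 80.1%.
- These figures take site as balanced between arms. A typical imbalance of 6.3 points at a 20% share gives a squared arm-site correlation of 0.063² × 0.25/0.16 = 0.6%. That lowers the no-effect figure to about 79.9%.

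**Adding site to the randomization instead.** Strata rise from 16 (mean 8 people) to 32 (mean 4). The chance of a difference of 6 or more, with a random MDACC count, falls from 18% to 9% with blocks of 4, but only from 19% to 17% with blocks of 8. With the count fixed at 26 and blocks of 8 it falls from 25% to 22%.

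**The case against.** The case on the other side is substantial.

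- **CT source stands in for site.** Much of the population contrast is screening versus non-screening CT, which 13.2 already stratifies. This holds in part: MDACC also recruits from screening and EIO from outside it, so each level mixes sites. It does reduce the imbalance. With 26 MDACC participants, a split of 8:18 or worse has a 4.7% chance without stratification and about 2.7% under 13.2 with the assumptions above.
- **The endpoint is within-person change.** Section 3 requires the same CT procedure at both time points, so a constant scanner offset largely cancels. The low-dose sections also share a 64-slice GE CT750 HD platform and a 2.5 mm thickness. This stands for fixed offsets. It does not cover differences in nodule natural history or in measurement error.
- **The effect is small.** The shift lies within the 0.28 mm standard error, and randomization keeps expected bias at zero. This stands.

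A reader might go further and infer that the list in 13.2 cannot run: boxes carry randomization numbers, stocks are separate, and "DCP does not permit the transfer of agents between institutions (unless prior approval from DCP is obtained"). The documents do not support that. The database issues the number. For US labels, section 6.6 states the language but not the content. The transfer rule covers DCP-supplied agent, whereas EIO stock comes from Bayer. Stocking every number at both sites, or reserving ranges by site, would work. The link between numbers and boxes is unstated, which is not the same as unworkable.

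**Conclusion.** The omission of site is complete and is plain from sections 13.2, 13.4 and 13.5. Its consequence is modest: a chance shift of at most about 0.03-0.17 mm at a 2-SD imbalance, set against a 0.8 mm target. There is no systematic bias, and the sample size is unaffected. These sizes rest on an assumed MDACC share of 10-33% and an assumed site difference of 0.3-1.0 mm, neither of which the documents give. The 18-22% chance of an arm difference of 6 or more rests on an assumed 20% share and blocks of 4.

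Adjusting for site is a free improvement. It removes chance site imbalance from the estimate, at a cost to power of about 0.2 percentage points or less in the typical case and with a gain of up to 3.5 points (80.1% to 83.6%). A claim that the trial is biased, or that its randomization is broken, would go beyond the documents.

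**What to change.** In 13.4, pre-specify site (EIO or MDACC) as a fixed effect in the primary between-arm comparison of change, for example a linear model of change on arm and site. Add the same term to the 13.5 models. Site is already recorded, so the cost is one degree of freedom and a short change of wording, which can be made before database lock.

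Separately, as clarification only, state in 6.6, 6.8 or 13.2 how randomization numbers map to boxes at each site.

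Site-specific lists are optional. They would create 32 strata of about 4 people on average, and the gain in balance depends on the unstated block size. If balance by site is wanted in the randomization, state the block size first. Minimization, or replacing one of the factors kept on conservative grounds, would avoid the extra strata.
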